4. INVESTIGATIONAL PLAN

4.1. Overall Study Design and Plan

DMID Protocol 17-0078 follows a Phase II randomized, partially-blinded study design enrolling males and non-pregnant females aged 19 to 50 years of age, inclusive, who are in good health as determined by medical history and physical examination, and meet all eligibility criteria, including erythrocyte sedimentation rate (ESR), hematology, and biochemistry parameter within acceptable range, and negative urine or serum pregnancy test (for females). This clinical trial is designed to assess the safety, reactogenicity and immunogenicity of one or two vaccinations of monovalent inactivated split influenza 2013 and 2017 A/H7N9 virus vaccines (2013 and 2017 A/H7N9 IIVs) manufactured by Sanofi Pasteur (SP), administered intramuscularly at different dosages (3.75 or 15 mcg of HA per dose), given with or without AS03 adjuvant manufactured by GlaxoSmithKline Biologicals (GSK), using different heterologous and homologous prime-boost vaccination schedules.

Subjects will be randomly assigned to 1 of 6 study groups with equal allocation 1:1:1:1:1:1 (see [Table 1](#)). Subjects assigned to Groups 1, 2, and 3 will receive an adjuvanted 2013 A/H7N9 IIV on Day 1 while those in Groups 4, 5, and 6 receive an adjuvanted 2017 A/H7N9 IIV on Day 1. Subjects assigned to Groups 1 and 4 will return approximately 21 days after their first vaccination to receive an adjuvanted 2017 A/H7N9 IIV. Subjects assigned to Groups 2,3,5, and 6 will return approximately after 120 days to receive their second vaccination of 2017 A/H7N9 IIV with or without AS03.

Reactogenicity will be measured by the occurrence of solicited injection site and systemic reactions from the time of each study vaccination through 7 days after each study vaccination. Unsolicited non-serious AEs will be collected from the time of each study vaccination through approximately 21 days after each study vaccination. SAEs and MAAEs, including NOCMCs and PIMMCs, will be collected from the time of the first study vaccination through approximately 12 months after the last study vaccination. Clinical laboratory evaluations for safety will be performed on venous blood collected prior to each study vaccination and approximately 7 days after each study vaccination.

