4.5.2. Immunogenicity Variables

Individual HAI and Neut results will be reported by the central immunology laboratory for the homologous 2013 A/H7N9 vaccine strain and 2017 A/H7N9 vaccine strain. Assay results are reported as a reciprocal titer with values of 10×2^k , where $k=0, 1, 2$, etc. The lower limit of detection (LLOD) for the HAI and Neut assays is 1:10; values below the limit of detection are imputed for analysis as one-half the limit of detection ($10/2 = 5$). For analysis, the geometric mean (calculated on natural log scale) of repeated results for each sample will be computed and used as the response for all subsequent calculations. The variation arising from multiple measurements for an individual at a single time point is not used in subsequent calculations. See Section 3.3 for definitions of derived variables for the analysis of HAI and Neut data. HAI and Neut data will be uploaded into the SDCC's electronic data capture system.

Frequency of strain-specific (2013 and 2017 A/H7N9) plasmablasts (IgA, IgG and IgM ASCs) will be characterized by the local laboratory using freshly collected PBMCs. A single frequency value will be reported, with a LLOD of 6 and an ULOD of 8000. Values below the LOD will be reported as one-half the LLOD ($6/2 = 3$). Values above the ULOD will be assessed for accuracy.

A plan for receipt of exploratory data will be determined with the assaying laboratories and documented in the SAP addendum.

The assay to determine the influenza virus N9 Neuraminidase (NA) antibody response to vaccination is under development. An addendum to the SAP will be generated to outline the planned analyses when assay development is complete and after receiving confirmation of this plan from DMID.

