5. SAMPLE SIZE CONSIDERATIONS

This study is planned to enroll up to 180 subjects. This study is not designed to test a formal null hypothesis. Rather, it is intended to obtain sufficient data to obtain meaningful estimates of the immune response and to uncover any safety issues that occur at a sufficiently high rate that they might be observed in a study of this size. As such, the type I error rate, $\alpha = 0.05$, is not adjusted for multiple comparisons. While this study is not designed to test any specific null hypothesis, the following tables illustrate the precision and power that is available for select estimates and comparisons of interest.

[Table 6](#) indicates the probability of observing one or more safety events, such as solicited injection site or systemic reactogenicity events or an unsolicited non-serious AE of a particular type for a single study group ($N = 30$), or in the trial as a whole ($N=180$).

Binomial confidence intervals (CI) are widest (have the least precision) when the response rate is 50%.

[Table 7](#) is presented to indicate the worst-case scenario for precision of observed exact (Clopper-Pearson) binomial confidence intervals.

[Table 8](#) illustrates the minimum detectable differences in the proportion of subjects responding (e.g. attaining seroconversion or a titer $\geq 1:40$) between any two study groups ($N=30$) using a two-sided Likelihood Ratio Test and $\alpha = 0.05$. It is assumed that up to 10% of subjects ($N=3$) will be excluded from the per protocol analysis. Seroconversion rates of 10% to 50% are considered.

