8.3.2. HAI and Neut Regression Modeling

Regression modeling will be utilized to test for the effect of treatment variables i.e. prime boost combination (*PrimeBoost*), Boost dose (*BoostDose*), and interval between vaccinations (*Interval*), on immune response. Logistic regression will be fit for the seroconversion outcome. If the available titer data meet the required assumptions of normality after log transformation, multiple linear regression will be fit to log-transformed titers. Separate models will be fit for each assay (HAI, Neut), each strain (2013 A/H7N9, 2017 A/H7N9) and each time point (Day 22 post vaccination 1, Day 22 post vaccination 2, Day 181 post vaccination 2). All models will be fit with a similar structure for *PrimeBoost*, *BoostDose*, *Interval*, and covariates, for the PP population. The treatment variables will be defined as *PrimeBoost* (homologous, heterologous), *BoostDose* (3.75 mcg+AS03, 15 mcg), and *Interval* (21 days, 120 days). All models will be fit with and without adjustment for the following covariates (*Z*): age in years, sex (female, male), BMI (<30, ≥ 30), and prior receipt of seasonal influenza vaccine in the current season (did not receive 2018-2019 seasonal influenza vaccine, received 2018-2019 seasonal influenza vaccine) (did not receive 2016-2017 or 2017-2018 seasonal influenza vaccines, received 2016-2017 and/or 2017-2018 seasonal influenza vaccine). The models as shown below assume a linear relationship between age in years and both probability of seroconversion and GMT. The validity of this assumption will be assessed prior to analysis and, if the relationship between age and response is found to be non-linear, adjustments will be made to model parameters to satisfy regression assumptions. Modeling assumptions will be checked using standard diagnostic methods (e.g., using the INFLUENCE option in PROC LOGISTIC or PROC GLM). Parameter estimates and odds ratio estimates for the logistic models will be presented for the 2013 and 2017 A/H7N9 strains without covariate adjustment in Table 64, Table 65, Table 66, Table 67, and with covariate adjustment in Table 68, Table 69, Table 70, Table 71. Parameter estimates for the multiple linear regression models will be presented for the 2013 and 2017 A/H7N9s strain without covariate adjustment in Table 72, Table 73, Table 74, Table 75, and with covariate adjustment in Table 76, Table 77, Table 78, Table 79.

Model 1A: Logistic Regression (without covariate adjustment):

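### The log-titer regressions (Models 2A/2B) pool one residual variance over six arms whose spread may differ, and name no remedy, so the BoostDose and Interval intervals can miss their nominal 95% coverage

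*SAP*

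**What the plan says.** SAP 8.3.2 makes the titer model conditional on one thing, "If the available titer data meet the required assumptions of normality after log transformation". If that is met, "multiple linear regression will be fit to log-transformed titers". Models 2A and 2B each carry a single error term, and the procedure named is PROC GLM. One residual variance for all six groups follows, although the SAP does not say so in words. For checking, the SAP says "Modeling assumptions will be checked using standard diagnostic methods (e.g., using the INFLUENCE option in PROC LOGISTIC or PROC GLM". The only departure that comes with a response is age: "if the relationship between age and response is found to be non-linear, adjustments will be made to model parameters to satisfy regression assumptions".

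SAP 4.5.2 handles undetectable titers by substitution: "values below the limit of detection are imputed for analysis as one-half the limit of detection". The limit is 1:10, so these values become 5.

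The shells for Tables 72-79 print coefficients with SE, CI and p-value, with Homologous, 15 mcg and 21 days as reference levels. A note on the Table 64 (logistic) shell drops interactions that are not significant, and the Table 72 shell has no interaction rows.

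**The concern.** A contrast between two arms should take its error from those arms. Under a pooled variance it borrows from all six. If spread differs by arm, the interval is too short for contrasts among the more variable arms and too long for contrasts among the less variable ones.

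The documents make unequal spread plausible. The floor at 5 compresses an arm with many undetectable titers. SAP 8.3.1 expects little or no antibody at baseline. The planning range in SAP Table 8 runs from 10% to 84% responders. Protocol 2.2 reports that the 2013 vaccine does not induce protective antibody against the newer lineage. The share of subjects at the floor could therefore differ by arm, assay strain and visit.

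Tables 24-31 give GMT intervals within each arm only. Tables 72-79 are the only planned between-arm titer estimates with intervals and p-values, and SAP 8.1 points to them from the primary immunogenicity analysis. The boost formulation and the dosing interval are stated goals of the trial (SAP 2).

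**Working it through.** **The plan's own figure.** SAP Table 8 gives the only two-arm power statement: 27 per arm, two-sided likelihood ratio test, alpha 0.05, 80% power. Full binomial enumeration gives 81.6%, 79.4%, 80.5%, 81.3% and 80.1% for its five rows, so the table is reproduced. It concerns proportions. Nothing comparable is stated for log titers, and no SD is given.

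**Which arms each coefficient uses.** Model 2A has six coefficients for six arms and is saturated. Inverting the design matrix gives:
- BoostDose = Group 5 - Group 6
- Interval = Group 5 - Group 4
- PrimeBoost = (1 - 2 + 3) - (4 - 5 + 6)
- each interaction uses four arms

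Without interactions, BoostDose and Interval each use four arms and PrimeBoost uses six.

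**Where pooling is harmless.** With equal n, pooled variance = mean of the six arm variances. PrimeBoost weights all six arms equally in absolute size, with or without interactions, so its pooled SE / true SE is 1.00 whatever the variances. Randomization supports equal n: "Subjects will be randomly assigned to 1 of 6 study groups with equal allocation 1:1:1:1:1:1". The exclusions expected in Protocol 11.4.2 leave about 30 x 0.90 = 27 in a 4-month arm and 30 x 0.95 = 28.5 in a 21-day arm, which is close to equal.

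**Spread differs by boost (assumed).** Let the SD be r in Groups 3 and 6 and 1 elsewhere.
- Pooled variance = (4 + 2r²)/6 = (2 + r²)/3
- BoostDose: pooled SE / true SE = sqrt[2(2 + r²) / (3(1 + r²))]
- Interval: pooled SE / true SE = sqrt[(2 + r²)/3]

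Simulated coverage of the nominal 95% interval (27 per arm, 156 df, 200,000 runs per contrast):

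| r | BoostDose ratio | Coverage | Interval ratio | Coverage |
|---|---|---|---|---|
| 0.5 | 1.095 | 96.8% | 0.866 | 91.1% |
| 1 | 1.00 | 95% | 1.00 | 95% |
| 1.5 | 0.934 | 93.2% | 1.190 | 98.0% |
| 2 | 0.894 | 92.0% | 1.414 | 99.4% |

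Dropping the interactions leaves these ratios unchanged, because both primes show the same pattern.

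**How far the floor can move the spread.** With a latent ln-titer SD of 0.8, 1.2 or 1.6 (assumed), substituting 5 makes the observed SD differ by a factor of 1.15, 1.54 or 1.92 between an arm with 10% and an arm with 95% of subjects at titer 40 or more.

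**Simulated titers (assumed: latent log2 SD 1.8, 28 per arm, two-fold grid, below 10 set to 5).**

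1. *Spread differs by prime only.* GMT is 80 in Groups 1-3 and 8 in Groups 4-6, giving observed SDs of about 1.80 and 1.30.
   - Pooled SD = sqrt[(1.80² + 1.30²)/2] = sqrt(2.465) = 1.570.
   - SE ratio in Groups 4-6 = 1.570/1.30 = 1.21. BoostDose and Interval cover about 98-99%, depending on how titers are rounded to the grid.
   - If the low arms are the heterologous ones, the reference arms have the larger SD. The ratio is 1.570/1.80 = 0.87 and coverage is about 90-91%.
   - Without interactions each contrast averages both primes. True and pooled variance are then both 2.465/n, and coverage is about 95%.
2. *Spread differs by boost or interval.* GMT is 15, 40 and 8 for 21-day, 4-month with AS03, and 15 mcg. Interval covers about 93% in both the full and the reduced model.
3. *Little censoring.* The two-arm contrasts examined cover 94.6-95.3%.

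HC3 standard errors gave about 95% in every scenario tried.

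**The case against.** **Checking is already promised.** Equal variance is a standard linear-model assumption, and the influence option is only an example. This stands in part: the SAP cannot be read as omitting checks. But influence diagnostics do not compare spread between arms, and no action is written for unequal variance.

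**Severe censoring may stop the model being fitted.** With up to 46% of an arm at the value 5, a Shapiro-Wilk test on residuals rejects in 96% of trials in scenario 1 and 98% in scenario 2. This is a fair point, but the SAP names no test or threshold, and Tables 72-79 are listed without condition.

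**Interactions will usually be dropped.** In scenario 1 there is no true interaction, and the reduced model would be used in about 90-92% of trials. That removes the problem there, but not in scenario 2.

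**Stronger readings.** A reader might infer several things that the documents do not support:
- *That the main error is false precision in the heterologous comparisons, Groups 1 v 2 and 2 v 3.* These are not printed coefficients. In scenario 1 the printed two-arm intervals are too wide, not too narrow.
- *That 93% coverage for Interval means an inflated type I error.* In that scenario the true GMTs are 15 and 40, so the null is false. The figure is non-coverage.
- *That the GMT intervals for individual arms are wrong.* Those in Tables 24-31 use Student's t for each group separately.
- *That arms differ in adjuvant at both doses.* All six are primed with AS03; only the boost differs.

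**Stakes.** The models sit in the exploratory section, and SAP 6.8 says no specific null hypothesis is tested. This stands and sets the severity.

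**Conclusion.** The concern holds in a limited form. Models 2A/2B imply one pooled residual variance, the plan's floor rule can make spread unequal, and no remedy is named. The exposed estimates are BoostDose and Interval. The error can go either way: from about 90-91% to 98-99% coverage when spread differs by prime and interactions are kept, and about 93% for Interval under the one boost/interval titer pattern simulated. That last case is the one that survives dropping the interactions.

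All these sizes rest on assumed GMTs and an assumed SD. Unequal variance is a reasoned possibility, not something the documents show. Severity is low.

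**What to change.** In SAP 8.3.2, state that Models 2A and 2B will be reported with HC3 standard errors, and that the SEs, CIs and p-values in Tables 72-79 come from these. The point estimates do not change.

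HC3 is preferable to a separate residual variance for each group: if every titer in an arm equals 5, that arm's variance is zero and the grouped-variance model is degenerate.

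The cost is one SAP sentence and a small program change. If variances are in fact equal, intervals widen very slightly. In the saturated Model 2A with 28 per arm the leverage is 1/28, so HC3 gives each arm mean a variance of s²/27 instead of s²/28. The SE is then larger by sqrt(28/27) = 1.018, or about 2%. Writing this in before unblinding also avoids choosing a remedy after seeing the titers.
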